9.3 Blinding and Randomization

Random numbers will be generated at a ratio of 1:1 (treatment group to control group) using the randomized block method by independent biostatisticians responsible for the data management and statistical analysis of this study. The selected block size and random seeds will be kept confidential. Statisticians unrelated to this study will label study drugs with the random number. Each study site will use the assigned code according to the sequence of enrollment.

This study will use the centralized randomization method and each study site will enroll subjects competitively. For each eligible subject, the study staff at study sites will log into the IWRS system, complete screening information, and obtain the random number and corresponding drug number. Investigators will dispense study drugs according to the random number and drug number.

9.4 General Considerations for Statistical Analysis

The quantitative variables will be summarized using number of subjects (n), mean, median, standard deviation, minimum and maximum. The qualitative variables will be summarized using counts and percentages. All summaries will be presented by treatment group. Summaries will be provided for demographics, baseline medical history, concurrent therapies, and subject disposition.

Medical history, concurrent therapies, and AEs will be coded to MedDRA and WHO Drug dictionaries.

Baseline measures are defined as the last measure before the initiation of study treatment, usually at Visit 2. If a measure is taken both pre-CAE[®] and post-CAE[®], the baseline will be the time point matched value at Visit 2. For measures from daily subject diaries, baseline is defined as the average of all days during the run-in period. For changes from pre-CAE[®] to post-CAE[®] post first treatment, the change from pre-CAE[®] to post-CAE[®] at Visit 2 will be considered the baseline value.

All analyses for primary and secondary efficacy outcomes will be tested 2-sided at a significance level of 0.05.

Unit of Analysis

Safety endpoints will be analyzed for both eyes. For efficacy endpoints, the unit of analysis will be the study eye, or the “worst eye,” as defined by the following:

Worst Eye: Eyes are eligible for analysis if they meet all of the inclusion criteria. In the case that both eyes are eligible for analysis, the worst eye will be the eye with worse (higher) inferior corneal staining pre-CAE[®] at Visit 2. If the inferior corneal staining is the same in both eyes, then the worst eye will be the eye with the highest ocular discomfort pre-CAE[®] at Visit 2. If the ocular discomfort is the same in both eyes, then the right eye will be selected as the worst eye.

9.5 Efficacy and Safety Analysis

9.5.1 Efficacy Analysis

9.5.1.1 Primary Efficacy Analyses

For primary efficacy endpoints, the pre- to post-CAE ICSS change will be calculated as post-CAE ICSS score-pre-CAE ICSS score. The change from baseline will be calculated as visit (post-CAE-pre-CAE)-baseline (post-CAE-pre-CAE) such that a positive difference indicates the change at study visit is larger than that at baseline. In addition, treatment comparisons between treatment and placebo groups will be calculated as treatment – placebo, such that a negative result indicates a better score for the treatment group (i.e., the treatment group have a smaller increase in dry eye signs or symptoms than the placebo group).

ANCOVA models will be used to compare the change from baseline in the pre- to post-CAE[®] inferior corneal fluorescein staining at Day 57 (Visit 6) (measured by the Ora Calibra[®] scale), between 0.25% HBM9036 Ophthalmic Solution and Placebo. The ANCOVA models will include the change in pre- to post-CAE ICSS at baseline as a covariate. The primary analysis will use LOCF imputation to have a full accounting of the FAS at the Day 57 visit, as described in Section 9.7.

9.5.1.2 Secondary Efficacy Analysis

The continuous and ordinal secondary efficacy variables collected at each visit will be summarized descriptively (n, mean, standard deviation, median, min and max), and analyzed with two-sample t-tests comparing the treatment group with placebo. All visit-based data will be analyzed at each visit and change from baseline. Change scores from pre- to post-CAE[®] will be calculated as post-CAE[®] score – pre-CAE[®] score. A Wilcoxon rank sum test and an ANCOVA model adjusting for baseline will also be assessed where appropriate. No imputation will be performed for secondary efficacy variables.

Two-sample t-tests and Wilcoxon rank sum tests will be used for ANCOVA model adjusting for baseline: the change from baseline in the pre- to post-CAE[®] change of the ICS fluorescein staining at Visit 5; the change from baseline in post-CAE[®] TF BUT and conjunctival redness; the change from baseline in unanesthetized Schirmer’s test results and OSDI scores at Visit 6; the change from baseline in pre-CAE[®] ocular discomfort (including

the Ora Calibra Dry Eye Ocular Discomfort Scale, Ora Calibra Ocular Discomfort and Dry Eye 4-Symptom Questionnaire) at Visits 5 and 6; the change from baseline in pre--CAE[®] burning sensation score assessed by VAS scale at Visit 6; and the change from baseline in the mean score of burning sensation by week assessed according to subject diaries.

The worst symptom for each subject will be identified as the symptom with the highest average score during the run-in period (Days -13 to 0) as recorded in the subject diary. The worst symptom and each individual symptom will be analyzed per day using a two-sample t-test. Additionally, the average score for the worst symptom and each individual symptom will also be analyzed separately using a Wilcoxon rank sum test.

9.5.2 Safety Analysis

Frequencies and percentages of subjects with treatment-emergent adverse events (TEAEs), serious TEAEs, and TEAEs causing premature discontinuation will be provided by treatment group. An AE is treatment emergent if it 1) occurs after the first dose of randomized study treatment or 2) if it is present prior to receipt of randomized study treatment but worsens in severity or increases in frequency after the first dose of randomized study treatment. Frequencies and percentages of subjects with AEs, SAEs, and AEs causing premature discontinuation will be provided by treatment group. The AEs will be listed by MedDRA SOCs and PTs and the AE listings will be categorized by severity, the causal relationship with study drug, and whether the AEs leading to discontinuation of study. No hypothesis test will be performed. Separate analyses will be performed for ocular specific and all AEs (including systemic).

Other safety endpoints including visual acuity, slit-lamp biomicroscopy, fundus color photography, drop tolerance, and intraocular pressure, will be summarized by treatment group and visit using descriptive statistics. Changes from baseline will also be summarized where appropriate. For assessments performed by eye, study eye and fellow eye will be summarized separately. In addition, shifts from baseline to worst on-treatment value will be summarized.

The exposure time (number of days) and drug administration times will be summarized by treatment group. The number and percentage of subjects with compliance will be calculated. The total exposure of the safety population will be summarized based on actual treatment received.

9.6 Subgroup Analyses

The four subgroups below are considered for subgroup analyses of primary efficacy outcome:

- Baseline subcorneal fluorescent staining score $<2, \geq 2$;
- Baseline conjunctival redness score $<2, \geq 2$;
- The course of disease is longer than average level, shorter than average level;

- The baseline CAE screening <20 minutes, ≥20 minutes.

The subgroup analyses above will be performed for secondary efficacy outcomes as appropriate.

9.7 Handling of Missing Data

The primary efficacy analyses will be performed using the Last Observation Carried Forward (LOCF) imputation method for missing values. For the analysis of ICSS at Day 57 (Visit 6), the last value from the previous visits will be carried forward, matching pre-CAE[®] or post-CAE[®] time points. A pre-CAE[®] time point will never be imputed for a post-CAE[®] value, and vice versa.

For the primary efficacy variables, the measured data will be used to assess the robustness of the study results.

No secondary efficacy endpoints or safety endpoints will be imputed.

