8.1.7 Visit 4: Day 15~~±2~~

There is no CAE[®] evaluation at Day 15, Visit 4.

- Subject diary/study drug collection. Subject diaries and all used study drug vials dispensed for Days 8 to 15 should be collected and reviewed by a trained study technician.
- Site staff must confirm subjects have not administered their morning placebo dose at home.
- Monitoring and query AEs
- Recording of all changes in concomitant medications
- Ora Calibra[®] Ocular Discomfort Scale
- Ora Calibra[®] Ocular Discomfort and 4-Symptom Questionnaire
- VAS discomfort scale
- OSDI
- BCVA Utilizing an ETDRS Chart
- Slit-lamp biomicroscopy
- Conjunctival redness
- TFBUT
- Corneal staining (fluorescein)
- Schirmer's test
- Subject diary. Prior to discharge from the study site on Visit 4 (Day 15), subjects will be educated in study drug diary recording and self-administration of study drug. Subjects will receive their assigned study drug kit with sufficient supply to last until Visit 5 and will be instructed not to self-administer study drug on the morning of their next scheduled study visit (Visit 5, Day 29).

- Schedule next visit. Subjects will be scheduled for Visit 5.

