9 STATISTICAL METHODS

9.1 Analysis Populations

The analysis populations in this study are defined as follows:

- **Full Analysis Set (FAS)** includes all the randomized subjects who have received at least one dose of study drug according to the principle of intention-to-treat (ITT). Subjects will be analyzed as randomized.
- **Per Protocol Set (PPS)** is a subset of the FAS population including all the subjects who do not have major protocol deviations and who complete the study. Subjects in the PP population will be analyzed as treated. Protocol deviations will be assessed before database lock and unblinding. For the subjects who have major protocol deviations (protocol violations), all their data should be eliminated from the PPS data, or the data of specific time points and/or subsequent time points should be eliminated.
- **Safety Set (SS)** includes all randomized subjects who have received at least one dose of the investigational product. The SS will be analyzed for all safety assessments. Subjects in the SS will be analyzed as treated.

In this study, the baseline data analysis will be based on the FAS. The efficacy analysis will be based on both FAS and PPS. The PPS will be used for main analysis. For the FAS, the missing data after dropout will be imputed using the Last Observation Carried Forward (LOCF) method. The observed and imputed data will be used for the analysis of FAS to assess the robustness of study results. The SS will be used for analysis of laboratory examination data, adverse events, and adverse reactions.

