6.2.2 Analysis Methods

An ANCOVA model will be used to compare $\Delta\Delta$ ICSS at Day 57 (Visit 6) (measured by the Ora Calibra[®] scale), between HBM9036 and placebo. The ANCOVA model will include treatment and baseline Δ ICSS as the only 2 covariates. The between-group differences in $\Delta\Delta$ ICSS, two-sided 95% confidence intervals (CIs), and p-value will be reported.

Two-sample t-test will be conducted as a sensitivity analysis.

The primary analysis will be performed on the PP populations. After obtaining data sets and calculating changes from baseline, the following SAS code will be used to run the ANCOVA model on data sets:

```
PROC MIXED DATA = OUTDATA;  
  CLASS TREATMENT;  
  MODEL CHANGE_INFERIOR = BASELINE TREATMENT / SOLUTION COVB;  
  LSMEANS TREATMENT / CL PDIFF;  
  ODS OUTPUT LSMEANS = OUTLS DIFFS = OUTDIFFS;  
RUN;
```

where

- *TREATMENT* is the name of the treatment group variable
- *BASELINE* is the baseline post-CAE[®] – pre-CAE[®] inferior corneal staining score in the study eye
- *CHANGE_INFERIOR* is the post-CAE[®] – pre-CAE[®] inferior corneal staining score in the study eye at Visit 6 (Day 57 ± 3) – *BASELINE*

Sensitivity analyses will be performed:

- on the FAS population using the last observation carried forward (LOCF) - imputation method for missing values will be used which means the last value from the previous visits will be carried forward, matching pre-CAE[®] or post-CAE[®] time points and a pre-CAE[®] time point will never be imputed for a post-CAE[®] value, and vice versa to have a full accounting of the FAS at the Day 57
- on the FAS using MMRM methodology

An example of the SAS code implementation of the ANCOVA model for the FAS population using LOCF is as follows:

```
PROC MIXED;  
    CLASS TREATMENT;  
    MODEL CHANGE_INFERIOR = BASELINE TREATMENT / SOLUTION COVB;  
    LSMEANS TREATMENT / CL PDIFF;  
RUN;
```

For LOCF, baseline value will be used for post baseline if both visit 5 and visit 6 are missing.

An example of the SAS code implementation of the ANCOVA model for the MMRM is as follows:

```
PROC MIXED;  
    CLASS TREATMENT PTNO VISIT;  
    MODEL CHANGE_INFERIOR = BASELINE TREATMENT VISIT VISIT*BAELINE  
    VISIT*TREATMENT/ DDFM=KR SOLUTION CHISQ;  
    REPEATED VISIT/SUBJECT=PTNO TYPE=UN R RCORR;  
    LSMEANS TREATMENT*VISIT / PDIFF=ALL OM CL ALPHA=0.05 SLICE=VISIT;  
RUN;
```

where

- *PTNO* is Patient number (ID)
- *VISIT* is visit timepoint (5, 6)

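### LOCF carries pre-CAE and post-CAE staining forward separately, so an imputed within-visit change can combine two different visits

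*Protocol*

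**What the plan says.** Protocol 9.5.1.1 computes the endpoint as "visit (post-CAE-pre-CAE)-baseline (post-CAE-pre-CAE) such that a positive difference indicates the change at study visit is larger than that at baseline". The quantity to be imputed at Visit 6 is therefore a post-minus-pre change within one visit.

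Protocol 9.7 imputes the scores, not the change: "the last value from the previous visits will be carried forward, matching pre-CAE" or post-CAE time points. Its one safeguard is "A pre-CAE[®] time point will never be imputed for a post-CAE[®] value, and vice versa". SAP 6.2.2 repeats both parts for the FAS and adds that "baseline value will be used for post baseline if both visit 5 and visit 6 are missing".

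Table 1 and section 8.1.7 of the protocol schedule corneal staining at Visit 4, where there is no CAE exposure. SAP 2.6 compares Visit 4 values with the pre-CAE baseline.

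The documents differ on the role of LOCF. Protocol 9.5.1.1 says "The primary analysis will use LOCF imputation to have a full accounting of the FAS at the Day 57 visit", and 9.7 agrees. Protocol 9.1 says "The PPS will be used for main analysis" and gives the imputed FAS analysis a robustness role. SAP 6.2.2 says "The primary analysis will be performed on the PP populations" and lists FAS LOCF and FAS MMRM as sensitivity analyses.

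**The concern.** The safeguard stops a pre-CAE score from standing in for a post-CAE score. It does not stop a post-CAE score from one visit being paired with a pre-CAE score from a later one. The result is not a response to any CAE exposure. It also contains the drift in pre-CAE staining between the two visits, with its sign reversed: a fall in pre-CAE staining enlarges the imputed change, which counts as worse, and a rise shrinks it.

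At stake is the meaning of the FAS analysis that is supposed to account for every treated subject. It is one of two FAS sensitivity analyses in the SAP, and the primary analysis on one reading of the protocol.

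**Working it through.** **The plan's own figures.** The documents give no figure for this rule. The nearest is the decision table in Protocol 9.2 and SAP 1.4. With SD 0.7 and 40 completers per arm, SE = 0.7 × √(2/40) = 0.1565, and a normal approximation gives all 15 cells to within 1 percentage point. For example, the No-Go probability at no effect is 73.85% against 73.8% stated, and the Go probability at 0.4 is 73.85% against 74.8%. The table concerns completers and does not bear on imputation.

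**Inputs.** Endpoint formula: Protocol 9.5.1.1. Carry-forward rule: Protocol 9.7 and SAP 6.2.2. Visits with CAE: 1, 2, 5 and 6; staining without CAE at Visit 4 (Table 1). Staining scale 0 to 4 in half grades (Appendix 1). The scores below are illustrations, written pre/post.

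**Route 1: lost after Visit 4, Protocol 9.7 only.** Visit 2 is 2.0/3.0 and Visit 4 is 1.5. Treat Visit 4 as a pre-CAE value, as SAP 2.6 does.
- Last post value: 3.0 (Visit 2). Last pre value: 1.5 (Visit 4).
- Change from baseline: (3.0 − 1.5) − (3.0 − 2.0) = +0.5.
- Carrying the Visit 2 pair: (3.0 − 2.0) − (3.0 − 2.0) = 0.
- SAP: Visits 5 and 6 are both missing, so baseline is used and the result is exactly 0. The route is closed.

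**Route 2: Visit 6 pre-CAE done, post-CAE missing, both documents.** Visit 5 is 2.0/3.0 and Visit 6 pre is 1.5.
- As written: 3.0 − 1.5 = 1.5.
- Visit 5 pair: 3.0 − 2.0 = 1.0.
- Opposite direction: if Visit 6 pre is 2.5, the result is 3.0 − 2.5 = 0.5, against 1.0.

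**Route 3: Visit 5 pre-CAE done, post-CAE missing, no Visit 6.** Visit 2 is 2.0/3.0 and Visit 5 pre is 1.5.
- Protocol: (3.0 − 1.5) − 1.0 = +0.5.
- SAP: the result depends on whether a half-completed Visit 5 counts as missing for the fallback, which is not stated.

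**General form.** Mixed minus paired = [post(old) − pre(new)] − [post(old) − pre(old)] = pre(old) − pre(new). The discrepancy is the fall in pre-CAE staining between the two visits.

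**Arm level, unadjusted means.** Let f be the share of an arm with mixed pairs and d the mean fall in pre-CAE staining among them. Relative to paired carry, the active-minus-placebo difference shifts by f(active) × d(active) − f(placebo) × d(placebo). It is zero when the two products are equal. None of the following inputs is in the documents:
- equal f of 5%, d larger on active by 0.25: 0.05 × 0.25 = 0.0125;
- equal f of 10%, d larger on active by 0.5: 0.10 × 0.5 = 0.05;
- f of 10% on active and 0 on placebo, d = 0.5: 0.10 × 0.5 = 0.05;
- one subject of 50 on active and none on placebo, d = 0.5: 0.02 × 0.5 = 0.01.

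The standard error with 50 per arm is 0.7 × √(2/50) = 0.14. A positive shift works against the active arm; reversing the imbalance reverses the sign.

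**The case against.** **The word matching could mean that the pair is carried.** No sentence says so, and the safeguard is written for separate pre and post values. The reading is possible but should not be left to the programmer.

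**Few subjects are affected under the SAP.** This stands. A subject who leaves before Visit 5 gets 0, and one who leaves after a complete Visit 5 carries an intact pair. The end-of-treatment column of Table 1 has no staining, so scheduled exit assessments create no half pairs. What remains is a CAE visit with staining before exposure but not after it.

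**The discrepancy is not an error against a known truth.** This also stands. In route 2 the Visit 6 post score is unknown. Had it been 3.0, the observed change would have been 1.5. The endpoint itself scores lower pre-CAE staining with unchanged post-CAE staining as worse. The defect is that the imputed value assumes the post-CAE score stayed still while the pre-CAE score moved, which no document justifies.

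**Two stronger readings are tempting.** A reader might infer that the rule works against the active drug, because all eight allergic-conjunctivitis withdrawals in the US study were on active (Protocol 1.4.2: three on 0.10%, five on 0.25%). That section gives neither arm sizes nor withdrawal dates. Under the SAP, early leavers are mostly not the subjects with mixed pairs.

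A reader might also infer that the zero fallback, set against the mean change of about 0.65 in Protocol 9.2, pulls the estimate across the −0.3 Go boundary. The 0.65 has no sign and no arm, so the result depends on how it is read and on an assumed dropout imbalance. The fallback also mixes no visits: paired carry gives the same 0 for anyone whose last CAE pair is Visit 2.

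**Conclusion.** The rule as written can produce a change score that belongs to no single visit, in both documents when a CAE visit is half completed, and in Protocol 9.7 also through Visit 4. For one subject the discrepancy equals the fall in pre-CAE staining between the two visits, 0.5 in the examples, and it can have either sign.

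At arm level, the illustrative imbalances shift the difference by about 0.01 to 0.05. These sizes rest on assumed frequencies and assumed pre-CAE changes. With no imbalance between arms, the rule adds noise and no bias.

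No Go-threshold crossing follows. The SAP's primary estimate is the PPS ANCOVA, and LOCF stands beside the MMRM as a sensitivity analysis. Protocol 9.5.1.1 and 9.7 call LOCF primary while 9.1 names the PPS, and those sections should be reconciled. This is a wording correction worth making, not a threat to the trial's conclusion.

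**What to change.** In Protocol 9.7 and SAP 6.2.2:

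- Carry forward only the paired post-minus-pre change from the last CAE visit with both values: Visit 5, otherwise Visit 2. Never use a Visit 4 value or one half of a pair.
- State that a CAE visit lacking either half counts as missing for this endpoint, including for the baseline fallback.
- Note that the fallback sets the change from baseline to exactly 0, so that readers of the FAS result know what was assumed.
- Keep the planned FAS MMRM alongside. It models within-visit changes at Visits 5 and 6 without imputation, so it has no mixed pairs. Which of the two FAS analyses ranks first is a matter of preference, and this point does not depend on it.

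The cost is a few sentences in two documents and a small change to one derivation, settled before database lock and unblinding. It needs no new data, no extra visits and no change in sample size.

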9.8 Interim analysis

No interim analysis will be conducted in this study.

9.9 Multiplicity Adjustment

No multiplicity adjustment is considered in this study.

9.10 Statistical Analysis Plan and Analysis Software

All the analyses will be described in detail in the Statistical Analysis Plan (SAP), and the shells of tables, data listings and figures will be attached. The SAP will be signed for approval before database locking and unblinding.

The SAS9.4 will be used for data processing, statistical screening, descriptive reporting and efficacy and safety analyses. The R3.5.1 software may also be used for plotting.

10 STUDY MANAGEMENT

10.1 Regulatory Authority Approval

Harbour BioMed will obtain approval to conduct the study from the appropriate regulatory agency in accordance with any applicable country-specific regulatory requirements before a study site initiates the study.

10.2 Ethical Conduct of the Study and Institutional Review Board/Independent Ethics Committee Approval

The study will be conducted in accordance with Good Clinical Practice (GCP). These standards respect the following guidelines:

- Guideline for Good Clinical Practice E6 (R1);
- Good Clinical Practice in China in current use;
- Declaration of Helsinki, concerning medical research in humans (Ethical Principles for Medical Research Involving Human Subjects);
- Any additional regulatory requirements.

The Investigator (or Harbour BioMed, where applicable) will be responsible for ensuring that this protocol, the site's ICF, and any other information that will be presented to potential subjects (e.g., advertisements or information that supports or supplements the ICF) will be reviewed and approved by the appropriate EC. The Investigator agrees to allow the EC direct access to all relevant documents. The EC must be constituted in accordance with all applicable regulatory requirements.

Harbour BioMed will provide the Investigator with relevant document(s)/data that are needed for EC review and approval of the study. If the protocol, the ICF, or any other information approved by EC and provided to potential subjects is amended during the study, the Investigator will be responsible for ensuring the EC reviews and approves, where applicable, these amended documents. The Investigator must follow all applicable regulatory requirements pertaining to the use of an amended ICF including obtaining EC approval of the amended form before new subjects consent to take part in the study using this version of the form. The EC approval of the amended ICF/other information and the approved amended ICF/other information must be forwarded to Harbour BioMed promptly.

